4.7.4 Adverse Events

All adverse events in patients who take at least one dose of EMPAGLIFLOZIN or DPP-4 inhibitor will be reported, encoded and categorized according to MedDRA version 21.1 and analysed. Relevant BICMQs will be considered. Specific adverse events to be evaluated in this study are detailed in section 4.7.5. Other adverse events of special interest (AESI) as listed in Study Protocol Section 11.1 will also be evaluated.

All the information collected in the AE form in the CRF and the SOC and preferred term corresponding to each reported term will be presented in listings.

Incidences will be summarized and displayed by System Organ Class and preferred term per period (see section 4.4) for:

- all AEs,

Statistical Analysis Plan (SAP)

Document Date: 17APR2019

Document Version: 1.0 Final

- AEs by relationship to medication (EMPAGLIFLOZIN or DPP-4 inhibitor)
- SAEs
- AESIs.

The summary tables will display the number and percentage of patients experiencing the respective event at least once as well as the number of occurrences. Percentages will be calculated with respect to the total number of patients in the Enrolled Set. If an event is reported more than once for a patient, the incidence of the strongest relationship to medication will be counted in the calculation of percentages (i.e. so each patient is only counted once for preferred term).

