Acute liver injury	Any the following criteria: An elevation of AST and/or ALT \geq 3-fold ULN combined with an elevation of bilirubin \geq 2-fold ULN measured in the same blood draw sample. An isolated elevation of AST and /or ALT \geq 5-fold ULN irrespective of any bilirubin elevation
Decreased renal function	Creatinine value shows a \geq 2-fold increase from baseline and is above the upper limit of normal (ULN)
ketoacidosis and diabetic ketoacidosis (DKA)	Defined as a serious condition because of inability of body cells to get glucose as a source of energy, and subsequently, the body produces ketones as the result of burning fat for energy. DKA occurs because of a lack of insulin in the body, not enough food intakes in diabetic patients and insulin reaction (low blood glucose). It is characterized by high ketones levels, positive ketones in the urine and high pH levels. Specifically, for the SGLT2i induced DKA the blood glucose level may not be increased above 240 mg/dl.
Events involving lower limb amputation	This definition includes amputation (i.e. resection of a limb through a bone), disarticulation (i.e. resection of a limb through a joint) and auto-amputations (i.e. spontaneous separation of non-viable portion of the lower limb). Not included in this definition are debridement (removal of callus or dead tissue), procedures on a stump (like stump revision, drainage of an abscess, wound revision etc.) and other procedures (e.g., nail resection or removal) without a concomitant resection of a limb (amputation or disarticulation).” Request to report each lower limb amputation as separate AE

ALT = alanine aminotransferase; ULN = upper limit of normal range.

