4.7.5 Ketoacidosis, severe UTI, depletion and dehydration

As main endpoints, ketoacidosis, severe UTI (namely pyelonephritis and urosepsis), volume depletion and dehydration, will be derived from corresponding AE reporting. Crude and treatment-adjusted incidence rates will be presented by group and period, together with incidence rate ratios of EMPAGLIFLOZIN relative to DPP-4 inhibitor, as point estimates and with 95% confidence limits. Treatment-adjusted incidence rates are defined as crude incidence rates per 1,000 person-years. Per group, and, where appropriate, per stratum and/or subgroup, the number of person-years is the sum of length of index periods of all respective patients.

For each endpoint, the time from index date to first occurrence in days is determined. If the endpoint does not occur for a patient, the time is right-censored by the duration of the respective period, index period or follow-up period. By group, times to first occurrence will be described by means of Kaplan-Meier estimates with 95% confidence limits and, where appropriate, median times with 95% confidence limits.

Crude and treatment-adjusted incidence rates and respective incidence rate ratios will be described in summary tables by group and period, and per period in subgroups by metformin status, GLD status and insulin status, respectively. Ratios are defined as Empagliflozin to DPP-4 inhibitors.

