5 LIST OF PLANNED TABLES, FIGURES AND LISTINGS

5.1 Tables

Table 5-1: Table of Content of Tables

No.	Title of the Table
1	Analysis Sets
2	Durations, Completion and Discontinuation of Follow-up
3	Demography
4.1	Medical History
4.2	Concomitant Diseases at Index Date

Statistical Analysis Plan (SAP)

Document Date: 17APR2019

Document Version: 1.0 Final

5.1	Prior Medication
5.2	Concomitant Medication at Index Date
6	Diagnosis and Complications
7	Renal Function Tests
8	Other Characteristics before and at Index Date
9	Treatment Exposure
10.1	HbA1c Measurements by Visit
10.2	Other Laboratory Tests by Visit
11.1	Concomitant Medication in Index Period
11.2	Concomitant Medication in Index Period during Ramadan
11.3	Concomitant Medication in Follow-up Period
11.4	Concomitant Medication in Follow-up Period during Ramadan
12.1	Adverse Event Summary in Index Period
12.2	Adverse Event Summary in Index Period during Ramadan
12.3	Adverse Event Summary in Follow-up Period
12.4	Adverse Event Summary in Follow-up Period during Ramadan
13.1	Incidence and Occurrence of Adverse Events in Index Period by SOC and PT
13.2	Incidence and Occurrence of Adverse Events in Index Period during Ramadan by SOC and PT
13.3	Incidence and Occurrence of Adverse Events in Follow-up Period by SOC and PT
13.4	Incidence and Occurrence of Adverse Events in Follow-up Period during Ramadan by SOC and PT
13.5	Incidence and Occurrence of Adverse Events in Index Period by BlcMQ
13.6	Incidence and Occurrence of Adverse Events in Index Period during Ramadan by BlcMQ
13.7	Incidence and Occurrence of Adverse Events in Follow-up Period by BlcMQ
13.8	Incidence and Occurrence of Adverse Events in Follow-up Period during Ramadan by BlcMQ
13.9	Incidence and Occurrence of Adverse Events of Special Interest in Index Period by SOC and PT
13.10	Incidence and Occurrence of Adverse Events of Special Interest in Index Period during Ramadan by SOC and PT

Statistical Analysis Plan (SAP)

Document Date: 17APR2019

Document Version: 1.0 Final

13.11	Incidence and Occurrence of Adverse Events of Special Interest in Follow-up Period by SOC and PT
13.12	Incidence and Occurrence of Adverse Events of Special Interest in Follow-up Period during Ramadan by SOC and PT
13.13	Incidence and Occurrence of Drug-Related Adverse Events in Index Period by SOC and PT
13.14	Incidence and Occurrence of Drug-Related Adverse Events in Index Period during Ramadan by SOC and PT

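### Acute liver injury, decreased renal function, amputation and SAEs are shown only as counts and crude percentages over periods of unequal length, with no promised patient-level row per special-interest event

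*SAP*

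**What the plan says.** Protocol 11.1, Table 1 defines four AESIs: acute liver injury, decreased renal function, ketoacidosis and lower limb amputation. SAP 4.7.4 takes them up: "Other adverse events of special interest (AESI) as listed in Study Protocol Section 11.1 will also be evaluated".

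The display is the same as for all adverse events. On layout, the SAP says "Incidences will be summarized and displayed by System Organ Class and preferred term per period". On content, it says "The summary tables will display the number and percentage of patients experiencing the respective event at least once as well as the number of occurrences". On the denominator, it says "Percentages will be calculated with respect to the total number of patients in the Enrolled Set". Within a table, each patient is counted once per preferred term.

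The table list in SAP 5.1 follows this. Table 13.9 is "Incidence and Occurrence of Adverse Events of Special Interest in Index Period by SOC and PT" and Table 13.11 is "Incidence and Occurrence of Adverse Events of Special Interest in Follow-up Period by SOC and PT". Tables 13.10 and 13.12 are the Ramadan counterparts, and Tables 13.17 to 13.20 do the same for SAEs.

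For ketoacidosis, severe UTI, volume depletion and dehydration, SAP 4.7.5 goes further. It plans rates per 1,000 person-years, incidence rate ratios, 95% confidence limits and Kaplan-Meier estimates, where "the number of person-years is the sum of length of index periods of all respective patients". Ketoacidosis is thus the only AESI with a person-time measure.

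**The concern.** A percentage of enrolled patients compares two groups fairly only if both are watched for about the same time. Here the main window is the index period, which SAP 4.4 ends with treatment. Protocol 9.9 itself warns of treatment changes caused by adverse effects of specific drugs. Protocol 7 names urinary and genital infections as reactions to empagliflozin. Unequal time on drug is therefore a possibility that the protocol raises, although it gives no figures.

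If one drug is stopped earlier, its percentage falls because it was observed for less time. A true excess could be muted, or equal risks could look different, beside main outcomes that are reported on a person-time scale.

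The second issue is counting. Table 1 defines each AESI as one clinical endpoint, but cases can be coded to several preferred terms. Acute liver injury has alternative AST, ALT and bilirubin criteria; amputation covers amputation, disarticulation and auto-amputation. A patient may appear in more than one row, so the rows cannot be added to give patients. The occurrence column does not help for amputation, because the protocol says "Request to report each lower limb amputation as separate AE".

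**Working it through.** **No figure to reproduce.** The documents give no AESI rate, no discontinuation rate and no expected time on drug. The only usable input is the target of 750 patients per group (SAP 4.2). Rates and times below are assumptions.

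**Do the follow-up tables equalise time?** SAP 4.4 runs follow-up to the end of observation. Protocol 9.7 refers to Protocol 9 for that end. Protocol 9 and SAP 3 stop follow-up at 12 months, death, the last supply plus 30 days, or a switch to the other index drug, among other conditions. On that text, follow-up also depends on treatment length, so Table 13.11 does not clearly remove the problem.

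**Formula.** Treat each group as observed for its mean time T with a constant rate λ.
- Crude proportion: p = 1 − exp(−λT).
- For rare events p ≈ λT, so the crude ratio ≈ (rate ratio) × (T empagliflozin / T DPP-4 inhibitor).

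**Main example: λ = 0.010 per year in both groups, T = 0.80 v 0.95 years.**
- Empagliflozin: 1 − exp(−0.0080) = 0.00797; × 750 = 6.0 patients.
- DPP-4 inhibitor: 1 − exp(−0.0095) = 0.00946; × 750 = 7.1 patients.
- Crude ratio: 0.00797 / 0.00946 = 0.84. Ratio of times: 0.80 / 0.95 = 0.84.
- Person-years to first event, 750 × p / λ: 597.6 v 709.1. Rates: 5.98 / 597.6 and 7.09 / 709.1, both 10.0 per 1,000, ratio 1.00.

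**Range, with a comparator rate of 10 per 1,000 person-years:**

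| Time, empagliflozin v DPP-4 (years) | True rate ratio | Crude percentage ratio |
|---|---|---|
| 0.80 v 0.95 | 1.00 | 0.84 |
| 0.80 v 0.95 | 1.30 | 1.09 |
| 0.85 v 0.90 | 1.30 | 1.23 |
| 0.90 v 0.75 | 1.00 | 1.20 |
| 0.90 v 0.60 | 1.00 | 1.50 |
| 1.00 v 1.00 | 1.00 | 1.00 |

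**Absolute size.** With 0.90 v 0.60 years and equal rates, the expected difference is about 0.4 patients at 2 per 1,000 and 1.1 at 5 per 1,000. At 10 per 1,000 it is 6.7 v 4.5 patients, and at 50 per 1,000 it is 33.0 v 22.2. For rare AESIs the shift is within chance.

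**The case against.** The AESIs in question are not study objectives. The four objectives get the full person-time treatment, and a descriptive count-and-percentage display of other safety data is conventional. No AESI test, ratio or interval is specified, so the plan itself draws no conclusion from the crude percentages. Time on drug is summarised by group (SAP 4.7.3, Table 9), as is length of follow-up (SAP 4.7.8, Table 2), so a reader can see unequal exposure. SAP 4.7.3 also counts patients who stopped more than 120 days before end of study, which suggests that observation may continue after stopping. Row splitting is inferred from table titles: the contents of summary Tables 12.1 to 12.4 are not shown, and Tables 13.5 to 13.8 group terms by BIcMQ. Person-time rates have limits too. They assume roughly constant risk, and Protocol 9.9 warns of risk that varies with duration.

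Most of this limits the size of the point. It does not remove it. Separate duration tables do not yield a first-event rate or its interval for any AESI. The 120-day category sits against the explicit stopping rules in Protocol 9 and SAP 3, so equal follow-up cannot be assumed. The BIcMQ tables may regroup some terms, but nothing ties them to the Table 1 definitions.

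A reader might go further and infer that AESIs are tabulated in the index period alone, or only as percentages. Neither is so: four periods are covered and occurrences are shown.

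**Conclusion.** The gap is real and worth closing. For three of the four Table 1 AESIs, and for SAEs, the plan has no person-time measure and no confidence interval. No table title promises one count of patients per AESI. SAP 4.7.5 already defines a person-time scale for the main outcomes.

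Its size depends on assumptions that the documents do not supply. The crude ratio moves by roughly the ratio of mean period lengths: 0.84 in the main example, which is about one patient in 750, and nothing if times are equal. It would be tempting to conclude that the study will misstate these harms. The documents do not support that, because they show no difference in time on drug and plan no inference on AESIs. Nor can it be said that every AESI will be left scattered over rows, since the BIcMQ or summary tables may gather some of the terms.

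**What to change.** Amend SAP 4.7.4 and Tables 13.9 to 13.12 as follows.

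1. Above the SOC/PT breakdown, add one row per Protocol Table 1 AESI, built from a pre-specified term list or named BIcMQ. Count each patient once, so that several amputations in one patient are one patient.
2. For each AESI and for SAEs, by group and for the index and follow-up periods, show patients with a first event, person-years to first event or end of period, and the rate per 1,000 person-years with an exact 95% CI. Person-years should stop at the first event; the sum of whole index periods in SAP 4.7.5 does not do this.
3. Keep the percentages, and state that the denominator is the group total (10 patients are 1.33% of 750 but 0.67% of 1,500).
4. Label the rates as descriptive and unadjusted for confounding.

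Period lengths are already derived in days (SAP 4.4), and Protocol 9.10.2.1 makes event onset dates mandatory. The cost is SAP wording, a term list and slightly longer tables. Two limits remain. The rates assume roughly constant risk. They also do not cure sparse laboratory ascertainment: SAP Table 3-1 lists other laboratory and renal tests at Visit 1 only, if available, while two of these AESIs are defined by laboratory thresholds.

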4.7.5 Ketoacidosis, severe UTI, depletion and dehydration

As main endpoints, ketoacidosis, severe UTI (namely pyelonephritis and urosepsis), volume depletion and dehydration, will be derived from corresponding AE reporting. Crude and treatment-adjusted incidence rates will be presented by group and period, together with incidence rate ratios of EMPAGLIFLOZIN relative to DPP-4 inhibitor, as point estimates and with 95% confidence limits. Treatment-adjusted incidence rates are defined as crude incidence rates per 1,000 person-years. Per group, and, where appropriate, per stratum and/or subgroup, the number of person-years is the sum of length of index periods of all respective patients.

For each endpoint, the time from index date to first occurrence in days is determined. If the endpoint does not occur for a patient, the time is right-censored by the duration of the respective period, index period or follow-up period. By group, times to first occurrence will be described by means of Kaplan-Meier estimates with 95% confidence limits and, where appropriate, median times with 95% confidence limits.

Crude and treatment-adjusted incidence rates and respective incidence rate ratios will be described in summary tables by group and period, and per period in subgroups by metformin status, GLD status and insulin status, respectively. Ratios are defined as Empagliflozin to DPP-4 inhibitors.

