Data analysis:	
For the incident users of Jardiance® (Empagliflozin) and of DPP4i, analysis will be performed using the “as-treated” (AT) approach. This corresponds to censoring individuals who discontinue use of the index drug, i.e. either switch from the index drug to any other of the index drug Jardiance® (Empagliflozin) or DPP-4 inhibitor during follow-up or stop using the index drug.
 
For the assessment of the primary and secondary objectives, the main data analysis will be conducted in two stages:
 
 - Construction of the propensity score (PS) by modelling the exposure Jardiance® (Empagliflozin) vs. DPP-4 inhibitor - Estimation of the effect of exposure to Jardiance® (Empagliflozin) on the ketoacidosis, severe urinary tract infections, volume depletion and dehydration compared to those exposed to DPP-4 inhibitor. 
Additional sensitivity analyses will be performed to validate the robustness of alternative definitions of outcome, exposure, covariates and reduction of bias due to matching.
 
The following estimates and comparison will be generated:
 
 - Crude and adjusted incidence rates of each of the outcomes among Jardiance® (Empagliflozin) new users and among DPP-4 inhibitor new users. Incidence rates will be reported as point estimates (in cases per 1,000 person-years) and 95% confidence intervals (CIs). - Summary IRRs, after adjusting (via stratified Mantel-Haenszel analysis) for propensity score deciles and calendar year, among Empagliflozin new users versus DPP-4 inhibitor new users - Adjusted IRRs for each of the outcomes will be the main effect estimates of interest. Adjusted incidence rates and IRRs will be calculated by weighting the incidence or IRR of each stratum (defined by propensity score decile and calendar year) by the amount of Jardiance® (Empagliflozin) person-time within the stratum - An additional analysis will further stratify the IRRs by categories of insulin use at the index date - Additional sensitivity analyses will be performed to evaluate potential for bias and confounding. 		

Name of company: [REDACTED]			
Name of finished medicinal product: Jardiance®			
Name of active ingredient: Empagliflozin			
Protocol date: 16 Oct 2017	Study number: 1245.149	Version/Revision: 3.0	Version/Revision date: 23 Sep 2019

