9.7.2 Main analysis using stratification

For the incident users of Empagliflozin along with their respective comparators, analysis will be performed using the “as-treated” (AT) approach. This corresponds to censoring individuals who discontinue use of the index drug, i.e. who either switch from the index drug to any other of the index drugs (Empagliflozin or DPP-4 inhibitor) during follow-up or who stop using the index drug. The AT approach is considering index periods.

For each event of interest, ketoacidosis, severe urinary tract infections, volume depletion, and dehydration, crude and adjusted incidence rates per cohort will be described and compared by means of incidence rate ratios (IRR). Incidence rates will be reported as point estimates and 95% confidence intervals (CIs). Crude incidence rates will be adjusted per 1,000 person-years. Per cohort and, where appropriate per stratum and/or subgroup, the number of person-years is the sum of length of index periods of all patients. Time to first event occurrence will be compared by means of hazard ratios and their 95% confidence intervals.

IRRs and hazard ratios are analysed using stratification. Strata are defined by PS quintiles. IRRs are investigated by means of a stratified Mantel-Haenszel analysis, while hazard ratios are investigated by means of a Cox regression, if proportional hazards can be assumed.

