5.2 Figures

Table 5-2: Table of Content of Figures

No.	Title of the Figure
1.1	Crude Incidence Rates of Primary Outcomes in Index Period
1.2	Crude Incidence Rates of Primary Outcomes in Index Period during Ramadan
1.3	Crude Incidence Rates of Primary Outcomes in Follow-up Period
1.4	Crude Incidence Rates of Primary Outcomes in Follow-up Period during Ramadan
2.1	Treatment-adjusted Incidence Rates of Primary Outcomes in Index Period
2.2	Treatment-adjusted Incidence Rates of Primary Outcomes in Index Period during Ramadan
2.3	Treatment-adjusted Incidence Rates of Primary Outcomes in Follow-up Period
2.4	Treatment-adjusted Incidence Rates of Primary Outcomes in Follow-up Period during Ramadan
3.1	Time to First Occurrence per Primary Outcome in Index Period – Kaplan-Meier plot
3.2	Time to First Occurrence per Primary Outcome in Follow-up Period – Kaplan-Meier plot
4.1	Propensity Scores in Enrolled Set – Box plot by Group and Subclass
4.2	Propensity Scores in Matched Set – Box plot by Group and Subclass

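### The incidence rates that the SAP labels 'treatment-adjusted' carry no confounder adjustment, and the visible text specifies no propensity-score-adjusted rate per group as the protocol abstract promises

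*SAP*

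**What the plan says.** The documents use the word 'adjusted' for rates in two ways.

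- **Protocol abstract (section 4, Data analysis).** It promises "Crude and adjusted incidence rates of each of the outcomes among" each cohort's new users and explains the adjustment: "Adjusted incidence rates and IRRs will be calculated by weighting the incidence or IRR of each stratum". Strata are PS decile by calendar year, and the weights are empagliflozin person-time. Adjusted incidence rate ratios (IRRs) are named as the main effect estimates.
- **Protocol 9.7.2.** It also promises that "crude and adjusted incidence rates per cohort will be described and compared by means of incidence rate ratios". The only adjustment it states for the rates themselves is "Crude incidence rates will be adjusted per 1,000 person-years". PS quintiles are attached to the IRRs and hazard ratios.
- **SAP 4.7.5.** "Crude and treatment-adjusted incidence rates will be presented by group and period", with rate ratios. The definition is "Treatment-adjusted incidence rates are defined as crude incidence rates per 1,000 person-years", and for the denominator, "the number of person-years is the sum of length of index periods of all respective patients". The same rates and their ratios are planned by metformin, glucose-lowering-drug and insulin status.
- **SAP 5.2.** Figures 1.1 to 1.4 show crude rates. Figures 2.1 to 2.4 are a separate set, the first titled "Treatment-adjusted Incidence Rates of Primary Outcomes in Index Period".
- **SAP 4.9.1, 4.10 and 5.1.** Endpoints are analysed within PS strata and pooled, the stratified Mantel-Haenszel analysis is kept, and stratified IRR and proportional-hazards tables are listed for all four outcomes (Tables 15.18 to 15.25, repeated in series 16 to 18).

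**The concern.** The primary objective is to estimate incidence in each group and compare the groups. Physicians choose the treatment, and the plan relies on the PS to deal with the resulting confounding. In that setting, a reader who sees an 'adjusted' rate beside a crude one in a figure, without SAP 4.7.5 to hand, may well assume that channelling has been addressed. As defined, it has not.

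Two things are at stake. A group-level estimate promised in the abstract may never be produced. And unadjusted rates for the primary outcomes may be read as confounder-adjusted. The point matters most in subgroups: SAP 4.7.5 plans rate ratios there, but no stratified IRR or hazard table is titled by subgroup.

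**Working it through.** The documents give no figure to reproduce: neither event rates by group nor covariate distributions are stated. The check is therefore a comparison of definitions, followed by an illustration on assumed inputs.

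**Definitions**

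| Source | What 'adjusted rate' means | Confounder control |
|---|---|---|
| Protocol abstract | stratum rates weighted by empagliflozin person-time | yes, via PS and calendar year |
| Protocol 9.7.2 | crude rate per 1,000 person-years | none |
| SAP 4.7.5 | crude rate per 1,000 person-years | none |

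Multiplying both groups' person-time rates by 1,000 leaves their ratio unchanged, so the SAP quantity and its ratio are unadjusted.

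**Does another planned output supply an adjusted rate per group?** Mantel-Haenszel pooling gives a ratio. The logistic regression in SAP 4.9.1 gives odds ratios, and the Cox model gives hazard ratios. Tables 15.18 to 15.21 are titled as stratified IRR analyses. None of these, as described, is a standardised rate for each group. The only outputs titled as adjusted rates are Figures 2.1 to 2.4.

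**What 'crude' means.** Because crude and 'treatment-adjusted' rates are separate figures, either they duplicate each other or the crude rate has some other denominator, such as patients. The SAP does not say.

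**Illustration (all inputs assumed).** Five PS strata of 300 patients, one person-year each, 750 patients per group, and the same outcome rate in both groups within every stratum (true IRR 1).

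| Stratum | Empagliflozin PY | DPP-4 PY | Rate per 1,000 PY |
|---|---|---|---|
| 1 | 90 | 210 | 5 |
| 2 | 120 | 180 | 10 |
| 3 | 150 | 150 | 15 |
| 4 | 180 | 120 | 20 |
| 5 | 210 | 90 | 25 |

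1. SAP 4.7.5 rate = 1,000 × events / person-years.
   - Empagliflozin: expected events 0.45 + 1.20 + 2.25 + 3.60 + 5.25 = 12.75; 12.75/750 × 1,000 = 17.0.
   - DPP-4 inhibitor: 1.05 + 1.80 + 2.25 + 2.40 + 2.25 = 9.75; 9.75/750 × 1,000 = 13.0.
   - Ratio: 17.0/13.0 = 1.31.
2. Abstract's rate = Σ wₖ × rateₖ, with wₖ the empagliflozin person-time share (0.12, 0.16, 0.20, 0.24, 0.28).
   - DPP-4 inhibitor: 0.6 + 1.6 + 3.0 + 4.8 + 7.0 = 17.0. Empagliflozin: 17.0. Ratio: 1.00.
3. Mantel-Haenszel IRR = Σ(aₖ × DPP-4 PYₖ/300) / Σ(bₖ × empagliflozin PYₖ/300), with aₖ and bₖ the empagliflozin and DPP-4 events: 5.175/5.175 = 1.00.

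Varying the assumptions gives this ratio of SAP-labelled rates (the abstract's ratio and the Mantel-Haenszel IRR stay at 1.00 in every case):

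| Empagliflozin patients, lowest to highest stratum | Rates 10 to 20 | Rates 5 to 25 |
|---|---|---|
| 150 to 150 | 1.00 | 1.00 |
| 120 to 180 | 1.07 | 1.14 |
| 90 to 210 | 1.14 | 1.31 |
| 60 to 240 | 1.22 | 1.50 |

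**The case against.** A reader might infer that the SAP has dropped confounder adjustment. The documents do not support that. SAP 4.7 is the descriptive section. The endpoint analysis is in SAP 4.9 onwards and is PS-stratified, so the IRR that the abstract calls the main effect estimate still has an adjusted analysis.

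Nor can it be said outright that an adjusted rate per group is not planned. Text after the first sentence of SAP 4.10 is blacked out, SAP 4.9.3 is not readable in the public copy, and 4.10 speaks of a stratified analysis of incidence rates. 'Not specified in the visible text' is as far as one can go.

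A reader might also infer that the SAP departed from the protocol on its own. In fact it follows protocol 9.7.2. The conflict is inside the protocol, between abstract and body.

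It is fair, too, that 'treatment-adjusted' may have been meant as adjusted for time on treatment, that its definition openly says crude, and that the SAP does not itself apply the term to the rate ratios. That lessens the risk of misreading but does not remove it, because figures are often read without their definitions. The view that the crude ratio is really a risk ratio is inference, since its denominator is not stated. Likewise, SAP 4.9.4 says the analyses will be repeated within subgroups, so adjusted subgroup ratios may exist even though no table title shows them.

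Finally, the illustration shows that any crude ratio can be confounded. It does not measure the effect of the label in this study.

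**Conclusion.** The point holds in a limited form. SAP 4.7.5 and Figures 2.1 to 2.4 put an 'adjusted' label on rates with no confounder control; protocol 9.7.2 and the abstract disagree on what an adjusted rate is; and no visible text or output title supplies the abstract's adjusted rate per group. What is affected is labelling and one promised group-level estimate, for four outcomes. The main PS-stratified comparison is not affected.

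The size of any misreading cannot be derived from the documents. The range 1.00 to 1.50 rests wholly on assumed strata, rates and equal person-time. This should be fixed, but it is not a fault that invalidates the analysis.

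**What to change.** 1. In SAP 4.7.5, Figures 2.1 to 2.4 and protocol 9.7.2, rename the quantity 'incidence rate per 1,000 person-years, unadjusted for confounders'. Label the SAP 4.7.5 rate ratios, including those by subgroup, as unadjusted.
2. State the denominator of the separate crude rate. If it is patients, present the result as a percentage.
3. Reconcile the abstract's decile-by-calendar-year strata with the quintiles in protocol 9.7 and the SAP.
4. Add, for the whole cohort, a PS-standardised rate per group with a 95% CI: Σ wₖ × rateₖ over the strata finally adopted, with the abstract's empagliflozin person-time weights. If events are too few for a stable estimate, say so in the report and record the omission in SAP 4.10.

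The cost is wording, relabelled outputs and one extra weighting step on strata already being formed. The statistical downside is wide intervals for rare outcomes such as ketoacidosis, for which protocol 9.9 already concedes that numbers may be low. Even in the illustration, with about 23 expected events (12.75 + 9.75 = 22.5), stratum counts by group run from 0.45 to 5.25.
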